3 DATA ANALYSIS CONSIDERATIONS

3.1 Timing of Analyses

No interim analysis is planned for this study.

Due to the decision to halt IMP dosing in this study, there are participants who did not complete the treatment period (up to Month 15), and therefore the primary data readout (per CSP V3.0) will not be required.

The final data readout will occur once all participants have completed the follow-up period (at Month 24) or early discontinuation visit at least 6 months after final dose of IMP due to early termination of the study (see CSP section 9.4).

3.2 Analysis Populations

Table 2: Populations for Analysis

Population/Analysis	Description
Enrolled	All participants who sign the ICF.
Full analysis set	All randomized participants who receive at least one dose of IMP. Participants will be assigned to their randomized treatment according to the intent-to-treat principle.
Safety analysis set	All participants who have received at least one dose of IMP. Participants will be assigned in this analysis set by the arm of treatment they actually received.
PK analysis set	All participants in the safety analysis set who received AZD7442 ¹ and who had at least one quantifiable serum PK observation post dose will be included in the PK analysis dataset. Participants will be assigned in this analysis set by the arm of treatment they actually received.
NLF PK analysis set	All participants in the safety analysis set who received AZD7442 ¹ and who had at least one quantifiable adjusted nasal lining fluid PK observation post dose will be included in the NLF PK analysis dataset. Participants will be assigned in this analysis set by the arm of treatment they actually received.
ADA evaluable analysis set	All participants in the safety analysis set who have a non-missing baseline AZD7442 ADA result and at least one non-missing post-baseline AZD7442 ADA result. This includes 2 separate evaluable analysis sets for AZD8895 and AZD1061. AZD7442 evaluable analysis set contains participants who are either AZD8895 evaluable or AZD1061 evaluable. Participants will be assigned in this analysis set by the arm of treatment they actually received.
nAb evaluable analysis set (Pseudovirus)	All participants in the safety analysis set who received AZD7442 ¹ , and who had at least one quantifiable serum observation (pseudovirus) post dose. Participants will be assigned in this analysis set by the arm of treatment they actually received.

Population/Analysis	Description
nAb evaluable analysis set (Authentic Virus)	All participants in the safety analysis set who received AZD7442 ¹ , and who had at least one quantifiable serum observation (authentic virus) post dose. Participants will be assigned in this analysis set by the arm of treatment they actually received.

Abbreviations: ICF, informed consent form; COVID-19, coronavirus disease 2019; IMP, investigational medicinal product.

¹As per participant-level exclusions from the analyses identified in the most recent version of the PDMP.

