9.3 Populations for Analyses

The following populations are defined in [Table 10](#).

Table 10 Populations for Analysis

Population/Analysis set	Description
Enrolled	All participants who sign the ICF.
Full analysis set	All randomized participants who receive at least one dose of IMP. Participants will be assigned according to their randomized treatment according to the intent-to-treat principle.
Safety analysis set	All participants who have received at least one dose of IMP. Participants will be assigned in this analysis set by the arm of treatment they actually received.
PK analysis set	All participants in the safety analysis set who received AZD7442 and who had at least one quantifiable serum PK observation post dose will be included in the PK analysis dataset.
ADA evaluable analysis set	All participants in the safety analysis set who have a non-missing baseline AZD7442 ADA result and at least one non-missing post-baseline AZD7442 ADA result.
nAb evaluable analysis set	All participants in the safety analysis set from whom blood samples are assumed not to be affected by factors such as protocol violations, and who had at least one quantifiable serum observation post dose. At any time during the study, participants will be excluded from this analysis set at the point at which they receive an alternative COVID-19 mAb.

ADA, antidrug antibody; COVID-19, coronavirus disease 2019; ICF, informed consent form; IMP, investigational medicinal product; nAb, neutralizing antibody; PK, pharmacokinetic.

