4.2.2.3 Handling of Dropouts and Missing Data

PK and PD analyses will be based on participants with data available. However, the following imputation methods will be used for descriptive analyses of PK and PD, respectively.

Pharmacokinetics data

Individual concentrations below the LLOQ of the bioanalytical assay will be reported as Not Quantifiable (NQ) in the listings with the LLOQ defined in the footnotes of the relevant tables, figures, and listings (TFLs). Serum concentrations that are NQ or not reported (NR) will be handled as follows for the provision of descriptive statistics:

- Any values reported as NR will be excluded from the summary tables and corresponding figures.
- At a time point where less than or equal to 50% of the concentration values are NQ, all NQ values will be set to the LLOQ, and all descriptive statistics will be calculated accordingly.
- At a time point where more than 50% (but not all) of the values are NQ, the mean, SD, geometric mean, gSD and geometric coefficient of variation (gCV%) will be set to Not Computed (NC). The maximum value will be reported from the individual data, and the minimum and median will be set to NQ.
- If all concentrations are NQ at a time point, no descriptive statistics will be calculated for that time point. The mean, minimum, median, and maximum will be reported as NQ and the gCV% and geometric mean and gSD as NC.
- The number of values below LLOQ ($n < \text{LLOQ}$) will be reported for each time point together with the total number of collected values (n).

- If only two observations are > LLOQ then the minimum and maximum are presented with the other summary statistics as NC.

SARS-CoV-2 Neutralizing Antibodies

The analysis of neutralizing antibody GMT and GMFR will use the following imputation method: a titer value measured below the LLOQ will be imputed to a value that is half of the LLOQ in summaries and analyses but will be listed as reported in the raw data. Titer values measured as above the upper limit of quantification (ULOQ) will be imputed at the ULOQ value.

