4.2.2.4.2 SARS-CoV-2 Neutralizing Antibodies

SARS-CoV-2 nAb analysis will be based on actual treatment in nAb Evaluable Analysis Set. Two (2) assays will be used to provide titers for authentic virus and pseudovirus nAb.

If a participant has any protocol deviation which is identified as a record-level exclusion for the immunogenicity analysis in Table 5 of the most recent version of the PDMP, then their SARS-CoV-2 nAb samples collected after the date of deviation will be excluded from the analyses.

Due to the change in dosing schedules between CSP V3.0 (dated 09 December 2022) and CSP V4.0 (dated 06 June 2023), there may be visits with a mixture of participants who received and participants who did not receive IMP in previous visit. Therefore, any SARS-CoV-2 nAb samples from participants who did not receive IMP according to the SoA of CSP V3.0, irrespective of the visit date being before or after the effective date of CSP V4.0, will be excluded from analyses at all subsequent visits.

SARS-CoV-2 nAb assessments scheduled for collection pre-dose, but instead collected post-dose at a visit where dosing is done, will be excluded from the analyses.

For participants who receive a COVID-19 vaccine after the first dose of IMP, data collected after receipt of the vaccine will also be excluded. Furthermore, for participant who receive a positive SARS-CoV-2 RT-PCR (defined in Section 4.2.3.4.1), data collected after infection will also be excluded, except in the case that SARS-CoV-2 nAb samples were collected during an illness visit.

Descriptive statistics for titer and fold rise will include number of participants, geometric mean, geometric standard deviation (gSD), 95% confidence interval (CI), minimum and maximum. This will be reported separately for nAbs collected during treatment period and illness visits (the illness visits where the series corresponds to positive RT-PCR test, as defined in Section 4.2.3.4.1, will be used in the summary).

A scatter plot of log₂ transformed titers with log₂ transformed serum concentration for each treatment arm, along with the bias-adjusted bootstrapped correlation coefficient, 95% CI and convergence (%) (see Section 4.2.2.2.1).

Summaries will also be split by the previous COVID-19 vaccination status (as defined in Section 4.1.5.1). Samples from 2 separate assays will be analysed using the same methods as described here.

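### Both nAb evaluable sets require a quantifiable post-dose titer, so a participant always below LLOQ is left out of the GMT and GMFR instead of being counted at LLOQ/2

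*SAP*

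**What the plan says.** SAP 3.2 (Table 2) defines two nAb sets, one per assay. Besides treatment with AZD7442, the first takes participants "who had at least one quantifiable serum observation (pseudovirus) post dose" and the second those "who had at least one quantifiable serum observation (authentic virus) post dose". Protocol 9.3 (Table 10) has a single nAb set with the same condition: "who had at least one quantifiable serum observation post dose".

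The GMT and GMFR are computed in these sets. SAP 4.2.2.4.2 states that "SARS-CoV-2 nAb analysis will be based on actual treatment in nAb Evaluable Analysis Set".

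SAP 4.2.2.3 gives a rule for results outside the assay range: "a titer value measured below the LLOQ will be imputed to a value that is half of the LLOQ in summaries and analyses". At the other end, "Titer values measured as above the upper limit of quantification (ULOQ) will be imputed at the ULOQ value".

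In the same Table 2, the ADA evaluable set asks only for a "non-missing baseline AZD7442 ADA result and at least one non-missing post-baseline AZD7442 ADA result". The serum PK and NLF PK sets use the quantifiable form, as the nAb sets do.

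SAP 4.1.2.2 will report, by arm, how many participants each set excludes and why. SAP 4.2.2.5 plans no sensitivity analysis for the PK or PD endpoints.

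**The concern.** Membership of the set is decided by the value of the endpoint. A participant who was dosed, sampled at every visit and always found below LLOQ has titer information, and the SAP has a rule for using it. The entry condition removes that participant before the rule can apply. LLOQ/2 imputation then reaches post-dose values only in participants who are quantifiable at some other post-dose visit.

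The GMT and GMFR would then describe participants with at least one measurable post-dose titer, not all participants dosed and sampled. A participant with no measurable neutralization after dosing is one that a pharmacodynamic endpoint ought to show. Because there is one set per assay, the two assays can also leave out different people.

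**Working it through.** **Inputs.** The entry rule comes from SAP Table 2 and the imputation at LLOQ/2 from SAP 4.2.2.3. SAP 4.2.2.2.2 defines the GMT as the antilog of the mean log2 titer over participants with titer information. The documents state no LLOQ, no expected GMT and no expected share of never-quantifiable participants, so these are assumed below. They contain no nAb design figure to reproduce. Their one design calculation is the chance of at least one AE in 100 participants at a true rate of 3%: 1 − 0.97^100 = 0.952, which agrees with the stated 95% but does not bear on this point.

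**GMT.** At a given visit, let f be the share of sampled participants who are never quantifiable after dosing. Each contributes LLOQ/2 if included. On the log scale the mean is a weighted average, so

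GMT(all) = GMT(set)^(1−f) × (LLOQ/2)^f

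and therefore

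GMT(set) / GMT(all) = [GMT(set) / (LLOQ/2)]^f.

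LLOQ/2 is the lowest value the analysis can assign, so this ratio is at least 1, and equals 1 when f = 0.

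**Numbers.** For GMT = 16 × LLOQ the base is 16 × 2 = 32; for GMT = 64 × LLOQ it is 64 × 2 = 128.

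| f | GMT = 16 × LLOQ | GMT = 64 × LLOQ |
|---|---|---|
| 0 | 1 | 1 |
| 1% | 32^0.01 = 1.035 | 128^0.01 = 1.050 |
| 5% | 32^0.05 = 1.189 | 128^0.05 = 1.275 |

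With 100 participants per arm, 1% is one person and 5% is five. A wider GMT range of 5 to 100 times LLOQ gives 10^0.05 = 1.12 to 200^0.05 = 1.30 at f = 5%.

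**GMFR.** An excluded participant has a post-dose value of LLOQ/2 and a pre-dose value of at least LLOQ/2, so the fold rise is at most 1. If the geometric mean fold rise of those excluded is R, then GMFR(set)/GMFR(all) = [GMFR(set)/R]^f. With R = 1 this is GMFR(set)^f: a GMFR of 32 gives the same 1.035 and 1.189 as above. If every baseline titer is at LLOQ/2, the GMT and GMFR factors are identical.

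**How large f could be.** The schedule of activities plans eight post-dose nAb samples in Arm A (Days 29, 92, 121, 183, 212, 274, 365, 456) and seven in Arm B (the same without Day 121), with fewer after early termination. One quantifiable result admits the participant. If each sample were below LLOQ with an assumed probability of 0.3, independently, the chance of never being quantifiable would be 0.3^3 = 0.027 with three samples and 0.3^8 = 0.00007 with eight. Titers within a person are likely to be correlated, which makes these figures too low, but they show that f falls as samples accumulate.

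**The case against.** The strongest reply is that the rule may exclude nobody. AZD7442 is given passively, at first doses of 600 mg IM or 1200 mg IV. Protocol 2.2 reports that in healthy adults 300 mg kept serum concentration above the protective threshold for 6 months in 96% of participants. That figure is for concentration, not titer, and for a different population, but it points to a small f. This stands as an argument about size. It does not show that f is zero. SAP 4.2.2.4.2 removes nAb records after certain deviations, vaccination, infection or missed dosing, so some participants may have few usable samples. The SAP does not say whether set entry is judged before or after those removals, and the assay strain is not stated.

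Two further points stand. The serum PK and NLF PK sets use the same quantifiable form, so the nAb rule follows a convention; and ADA results are reported as positive or negative, so the ADA set is a weaker comparator. A shared convention does not make outcome-dependent entry sound where an imputation rule is already in place.

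The endpoint is descriptive, with no hypothesis test, so no error rate is affected. At f = 1% the shift is also smaller than sampling error. With an assumed geometric SD of 2 to 4 and n = 100, the upper 95% limit lies a factor of exp(1.96 × ln 2 / 10) = 1.15 to exp(1.96 × ln 4 / 10) = 1.31 above the GMT. Reporting the exclusions by arm would make any loss visible, but it leaves the GMT as it is.

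A reader might infer that the set definition contradicts the imputation rule. It does not: the LLOQ/2 rule still applies to baseline titers and to low values at single visits. The definition only prevents the rule from reaching never-quantifiable participants.

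**Conclusion.** The point holds as a minor flaw in the analysis-set definition. A dosed, sampled participant who is below LLOQ at every post-dose visit is left out of the GMT and GMFR, and no planned analysis puts that participant back. The overstatement is nil if there are no such participants, about 3.5 to 5% at f = 1%, and about 19 to 27% at f = 5%. These figures rest on an assumed GMT of 16 to 64 times LLOQ; the values of f are scenarios, and a small one is the more likely.

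Two stronger readings are tempting, and the documents support neither.

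- That the plan removes non-responders generally, or every low titer. Only participants who are never quantifiable are lost, and 'responder' is a loose word for a passively given antibody.
- That the reported GMT is bound to be too high. This needs at least one excluded participant, and nothing in the documents shows that there will be one. 'Quantifiable' is also undefined for values above ULOQ. If such values count as not quantifiable, a participant with only those would be dropped too, which pulls the GMT down. The upward direction is certain only for the below-LLOQ exclusion.

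**What to change.** In SAP Table 2, replace 'quantifiable' with 'non-missing' in both nAb evaluable set definitions. Values below LLOQ and above ULOQ are then handled by the imputation already in SAP 4.2.2.3, and the question of what counts as quantifiable no longer affects set entry. State whether set entry is judged before or after the record-level removals in SAP 4.2.2.4.2.

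Record the departure from protocol Table 10 in SAP Section 2, which already documents another change to this set. No protocol amendment is needed.

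The cost is one word per definition and a sentence in Section 2. The GMT and GMFR may be slightly lower, and the nAb sets will differ in form from the PK sets. The PK–nAb correlation is unaffected, because it uses only paired quantifiable records. If no participant is always outside the quantifiable range, the results do not change.

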3.3 General Considerations

Categorical variables will be summarized using frequency and percentages, where the denominator for calculation is the underlying analysis set population, unless otherwise stated. A row denoted as “Missing” will be included in the count tabulations where necessary to account for missing values. Summaries will be provided by treatment and visit when applicable.

Continuous variables may be summarized with descriptive statistics of number of participants with available data (n), mean, standard deviation (SD), median, the first quartile (Q1), third quartile (Q3), minimum and maximum. Summaries will be provided by treatment and visit when applicable.

For concentration data and log-transformed data, descriptive statistics (i.e., n and n < lower limit of quantification (LLOQ) [number of participants with available result and number of participants with results below the limit of quantification], geometric mean, geometric SD, arithmetic mean, SD, co-efficient of variation, median, min and max) will be presented by treatment group and visit, when applicable.

3.3.1 General Study Level Definitions

Reference start date and study day

Study Day will be calculated from the reference start date and will be used to show start/stop day of assessments and events. Reference start date is defined as the first day of the dose of IMP i.e., Day 1.

Study Day will be computed as follows:

- *Study Day = (Date of assessment/event – Date of first dose of IMP) + 1 if the date of the assessment/event is on or after the date of the first dose of IMP.*

- *Study Day = (Date of assessment/event – Date of first dose of IMP) if the date of the assessment/event is prior to the date of the first dose of IMP.*

In general, when the assessment/event date is partial or missing, Study Day and any corresponding durations will be displayed as missing in the listings.

For illness visits, an illness study day will be calculated. The reference start date is defined as the day of first illness assessment, i.e., illness visit Day 1. This will be calculated separately for each illness episode.

Illness Study Day will be computed as follows:

- *Illness Study Day = (Date of assessment/event – Date of illness visit Day 1) + 1.*

Baseline

In general, baseline is defined as the last non-missing measurement taken prior to the first dose of IMP. If the last non-missing measurement is taken at same date and time of the dose of IMP, this measurement will be considered baseline, with the exception of adverse events (AEs) and non-IMP medications commencing on the date and time of the dose of IMP, these assessments will be considered post-baseline.

Illness Visit baseline is defined as the first non-missing measurement taken on Illness Visit Day 1. If there is no non-missing measurement available on Illness Visit Day 1, Illness Visit baseline is considered as missing. For instances, where Illness Visit Day 1 occurs on the same day as a main study Visit, and Illness Visit Day 1 measurements are missing, then the measurements from the main study Visit will be used as Illness Visit baseline. Otherwise, if there is still no available measurement for Illness Visit Day 1, Illness Visit baseline is considered as missing.

Change from baseline will be calculated as (*post-baseline visit – baseline visit*).

Change from baseline for Illness Visits will be calculated as:

- *Change from baseline at Illness Visit Day 1 = Test value at Illness Visit Day 1 – Baseline value*
- *Change from baseline at Illness Visits after Illness Visit Day 1 = Test value at post Illness Visit – Illness Visit baseline value*

3.3.2 Visit Window

A windowing convention will be used to determine the analysis value for a given study visit for visit-based assessments, which are as follows:

- Serum sample for SARS-CoV-2 serology (anti-nucleocapsid testing)
- Serum sample for AZD7442 PK assessments
- Serum sample for AZD7442 ADA
- Serum sample for SARS-CoV-2 nAbs levels (pharmacodynamics [PD])
- Serum sample exploratory biomarkers
- Nasal lining fluid sample for AZD7442 PK assessments
- Clinical chemistry, hematology, coagulation, and urinalysis
- Vital signs
- Electrocardiogram (ECG)
- Illness visits for COVID-19 symptom assessment, vital signs, immunogenicity, PD, PK, coagulation, serum sample for exploratory assessments

The window for the visits following baseline will be constructed in such a way that the upper limit of the interval falls halfway between the two visits (the lower limit of the first post-baseline visit will be Day 2). If an odd number of days exists between two consecutive visits, then the upper limit will be taken as the midpoint value minus 1 day.

One or more results for a particular variable may be obtained in the same visit window. In such an event, the result with the date closest to the expected visit date will be used in the analysis. In the event that two observations are equidistant from the expected visit date, the later observation will be used in the analysis.

The visit windows are defined in the following tables.

Table 3: Analysis windows for serum sample for SARS-CoV-2 serology, ADA and SARS-CoV-2 nAbs levels

Arm A

Visit	Day Relative to First Dose	Visit Window (Study Day)
Day 1	≤ 1	≤ 1
Day 29	29	2 – 60
Day 92	92	61 - 106
Day 121	121	107 - 152
Day 183	183	153 - 197
Day 212	212	198 - 242
Day 274	274	243 - 319
Day 365	365	320 - 410
Day 456	456	≥411 [for serology and SARS-CoV-2 nAbs] 411 – 592 [for ADA assessment]
Day 729 (Follow-up)	729	≥593 [for ADA assessment]

Arm B

Visit	Day Relative to First Dose	Visit Window (Study Day)
Day 1	≤ 1	≤ 1
Day 29	29	2 – 60
Day 92	92	61 - 137
Day 183	183	138 - 197
Day 212	212	198 - 242
Day 274	274	243 - 319
Day 365	365	320 - 410
Day 456	456	≥411 [for serology and SARS-CoV-2 nAbs] 411 – 592 [for ADA assessment]
Day 729 (Follow-up)	729	≥593 [for ADA assessment]

Table 4: Analysis windows for serum sample for AZD7442 PK assessment, NLF sample for mucosal response

Arm A

Visit	Day Relative to First Dose	Visit Window (Study Day)
Day 3	3	2 – 6 [subset of 20 participants, PK and NLF assessment]
Day 11	11	7 – 19 [subset of 20 participants, PK and NLF assessment]
Day 29	29	20 – 60 [subset of 20 participants, PK and NLF assessment] 2 – 60 [otherwise]
Day 92	92	61 - 106
Day 121	121	107 - 152
Day 183	183	153 - 197
Day 212	212	198 - 242
Day 274	274	243 - 319
Day 365	365	320 - 410
Day 456	456	≥411

Arm B

Visit	Day Relative to First Dose	Visit Window (Study Day)
Day 1, Post-dose	1	1, > 1 st IMP dose time
Day 3	3	2 – 6 [subset of 20 participants, PK and NLF assessment]

Visit	Day Relative to First Dose	Visit Window (Study Day)
Day 11	11	7 – 19 [subset of 20 participants, PK and NLF assessment]
Day 29	29	20 – 60 [subset of 20 participants, PK and NLF assessment] 2 – 60 [otherwise]
Day 92	92	61 - 137
Day 183	183	138 - 197
Day 212	212	198 - 242
Day 274	274	243 - 319
Day 365	365	320 - 410
Day 456	456	≥411

Table 5: Analysis windows for cardiac/thrombosis biomarkers

Visit	Day Relative to First Dose	Visit Window (Study Day)
Day 1	≤ 1	≤ 1
Day 29	29	2 - 60
Day 92	92	61 - 137
Day 183	183	138 - 228
Day 274	274	229 - 319
Day 365	365	320 - 410
Day 456	456	411 - 592
Day 729 (Follow-up)	729	≥593

Table 6: Analysis windows for clinical chemistry, hematology, coagulation, and urinalysis

Visit	Day Relative to First Dose	Visit Window (Study Day)
Day 1	≤ 1	≤ 1
Day 92	92	2 - 137
Day 183	183	138 - 228
Day 274	274	229 - 319
Day 365	365	320 - 410
Day 456	456	411 - 592
Day 729 (Follow-up)	729	≥593

Table 7: Analysis windows for Vital signs

Arm A

Visit	Day Relative to First Dose	Visit Window (Study Day)
Screening	<1	<1
Day 1, Pre-dose	1	1, ≤ 1 st IMP dose time
Day 1, Post-dose	1	1, > 1 st IMP dose time
Day 29	29	2 - 60
Day 92, Pre-dose	92	61 – 106, ≤ 2 nd IMP dose time
Day 92, Post-dose	92	61 – 106, > 2 nd IMP dose time
Day 121	121	107 - 151
Day 183, Pre-dose	183	152 – 197, ≤ 3 rd IMP dose time
Day 183, Post-dose	183	152 – 197, > 3 rd IMP dose time
Day 212	212	198 - 242
Day 274, Pre-dose	274	243 – 319, ≤ 4 th IMP dose time
Day 274, Post-dose	274	243 – 319, > 4 th IMP dose time
Day 365, Pre-dose	365	320 – 410, ≤ 5 th IMP dose time
Day 365, Post-dose	365	320 – 410, > 5 th IMP dose time
Day 456	456	411 - 592
Day 729 (Follow-up)	729	≥593

Arm B

Visit	Day Relative to First Dose	Visit Window (Study Day)
Screening	<1	<1
Day 1, Pre-dose	1	1, ≤ 1 st IMP dose time
Day 1, During Dose, 15 mins	1	>1 st IMP dose time - ≤ 22 minutes 30 seconds post 1 st IMP dose time
Day 1, During Dose, 30 mins	1	>22 minutes 30 seconds post 1 st IMP dose time - ≤ 37 minutes 30 seconds minutes post 1 st IMP dose time
Day 1, During Dose, 45 mins	1	>37 minutes 30 seconds post 1 st IMP dose time - ≤ 52 minutes 30 seconds post 1 st IMP dose time
Day 1, During Dose, 60 mins	1	> 52 minutes 30 seconds post 1 st IMP dose time - ≤ 67 minutes 30 seconds post 1 st IMP dose time
Day 1, Post-dose	1	1, >67 minutes 30 seconds post 1 st IMP dose time
Day 29	29	2 - 60
Day 92	92	61 - 137
Day 183, Pre-dose	183	138 – 197, ≤ 2 nd IMP dose time
Day 183, Post-dose	183	138 – 197, > 2 nd IMP dose time

Visit	Day Relative to First Dose	Visit Window (Study Day)
Day 212	212	198 - 242
Day 274	274	243 - 319
Day 365, Pre-dose	365	320 – 410, \leq 3 rd IMP dose time
Day 365, Post-dose	365	320 – 410, $>$ 3 rd IMP dose time
Day 456	456	411 - 592
Day 729 (Follow-up)	729	\geq 593

Table 8: Analysis windows for ECG

Arm A

Visit	Day Relative to First Dose	Visit Window (Study Day)
Screening	<1	<1
Day 1	1	1
Day 92	92	2 - 137
Day 183	183	138 - 228
Day 274	274	229 - 319
Day 365	365	320 - 410
Day 456	456	\geq 411

Arm B

Visit	Day Relative to First Dose	Visit Window (Study Day)
Screening	<1	<1
Day 1	1	1
Day 183	183	2 - 273
Day 365	365	274 - 410
Day 456	456	\geq 411

Table 9: Analysis windows for immunogenicity, PD, PK, coagulation, serum sample for exploratory assessments (Illness visit schedule)

Visit	Day Relative to Illness	Visit Window (Study Day)
Illness Day 1	≤ 1	≤ 1
Illness Day 14	14	≥ 2

Table 10: Analysis windows for COVID-19 symptom assessment, SARS-CoV-2 RT-PCR sequencing NP swab, and vital signs (for Confirmed Illness visit schedule)

Visit	Day Relative to Illness	Visit Window (Study Day)
Illness Day 1	≤ 1	≤ 1

Visit	Day Relative to Illness	Visit Window (Study Day)
Illness Day 5	5	2- 5
Illness Day 7	7	6 - 10
Illness Day 14	14	≥11 (for Vital signs) 11 – 20 (for Covid-19 symptoms)
Illness Day 28	28	21 – 58 (for Covid-19 symptoms)
Illness Day 90	90	≥59 (for Covid-19 symptoms)

For assessments occurring during the Illness Visit Schedule, windows are applied only to illness episodes with laboratory confirmed positive RT-PCR test results. One or more results for a particular human biological samples variable may be obtained in the same visit window. In such an event, the result with the date closest to the expected visit date will be used in the analysis. In the event that two observations are equidistant from the expected visit date, the later observation will be used in the analysis.

